8.6.1.1 Event-Free Survival

The non-parametric Kaplan-Meier method will be used to estimate the EFS curve in each treatment group. The hypothesis of treatment difference in EFS will be tested by the stratified log -rank test. A stratified Cox proportional hazard model with Efron's method of tie handling will be used to estimate the magnitude of the treatment difference (i.e., HR) between the treatment arms. The HR and its 95% CI from the stratified Cox model with Efron's method of tie handling and with a single treatment covariate will be reported. The stratification factors used for randomization (RT regimen, tumor site/p16 status and stage, see Section 5.6 for additional detail) will be applied to both the stratified log-rank test and the stratified Cox model. In the event that there are a small number of events in one or more strata, for the purpose of analysis, strata will be combined to ensure sufficient number of events in each stratum. Details regarding the combining of strata will be specified in the sSAP prior to database lock based on a blinded review of event counts by stratum.

Since disease progression is assessed periodically, disease progression can occur any time in the time interval between the last assessment where PD was not documented and the assessment when PD is first documented. For the primary analysis, for the subjects who have PD, the true date of the EFS event will be approximated by the date of the first assessment at which PD, surgery, or death is objectively documented.

In order to evaluate the robustness of the EFS endpoint, one primary and three sensitivity analyses with a different set of censoring rules will be performed. The primary analysis

follows the intention-to-treat principle. That is, PD, surgery or death is counted as event regardless of missed study visits or initiation of new anticancer therapy. For the first sensitivity analysis, if the events (PD, surgery or death) are after the initiation of a new anticancer therapy for R/M disease, the data are censored at the last disease assessment prior to the initiation of a new anticancer therapy for R/M disease. The second sensitivity analysis considers initiation of a new anticancer treatment for R/M disease to be an EFS event for subjects without a documented EFS event. The third sensitivity analysis is the same as the primary EFS analysis, with the exception that surgery is not counted as an EFS event. If a subject meets multiple criteria for censoring, the censoring criterion that occurs earliest will be applied. The censoring rules for primary and sensitivity analyses are summarized in [Table 24](#).

Table 24 Censoring Rules for Primary and Sensitivity Analyses of EFS

Situation	Primary Analysis	Sensitivity Analysis 1	Sensitivity Analysis 2	Sensitivity Analysis 3
PD, surgery or death documented before new anticancer therapy* if any, or new anticancer therapy is not initiated	EFS event at date of documented PD, surgery or death	EFS event at date of documented PD, surgery, or death	EFS event at date of documented PD, surgery or death	EFS event at date of documented PD or death. If no PD and no death, censored at last disease assessment.
PD, surgery or death documented after new anticancer therapy*	EFS event at date of documented PD, surgery or death	If the new anticancer therapy is for R/M disease, then censored at last disease assessment before the initiation of a new anticancer therapy for R/M disease; otherwise, EFS event at date of documented PD, surgery or death	EFS event at date of documented PD, surgery, death, initiation of a new anticancer therapy for R/M disease, whichever occurs first.	EFS event at date of documented PD or death. If no PD and no death, censored at last disease assessment.
No PD, no surgery and no death; new anticancer therapy* is not initiated	Censored at last disease assessment	Censored at last disease assessment	Censored at last disease assessment	Censored at last disease assessment
No PD, no surgery and no death; new anticancer therapy* is initiated	Censored at last disease assessment	If the new anticancer therapy is for R/M disease, then censored at last disease assessment before the initiation of a new anticancer therapy for R/M disease; otherwise, censored at last disease assessment	If the new anticancer therapy is for R/M disease, then EFS event at date of the initiation of a new anticancer therapy for R/M disease; otherwise, censored at last disease assessment	Censored at last disease assessment
EFS= event free survival; PD=progressive disease; R/M=recurrent or metastatic. * The new anticancer therapy in the sensitivity analyses 1 and 2 is defined as any new oncology drugs or radiation for R/M disease.				

8.6.1.2 Overall Survival

The non-parametric Kaplan-Meier method will be used to estimate the survival curves. The hypothesis of a treatment difference in OS will be tested by the stratified log -rank test. A stratified Cox proportional hazard model with Efron's method of tie handling will be used to estimate the magnitude of the treatment difference (i.e., the HR) for OS. The HR and its 95% CI from the stratified Cox model with a single treatment covariate will be reported. The stratification factors used for randomization will be applied. In the event that there are a small number of events in one or more strata, for the purpose of analysis, strata will be combined to ensure sufficient number of events in each stratum. Details regarding the combining of strata will be specified in the sSAP prior to database lock based on a blinded review of event counts by stratum.

8.6.2 Summary of Efficacy Analysis Methods

A summary of the analysis strategy for key efficacy endpoints is provided in [Table 25](#).

Table 25 Analysis Strategy for Key Efficacy Endpoints

Endpoint/ Variable	Statistical Method [†]	Analysis Population	Missing Data Approach
Primary Hypothesis			
EFS	Test: Stratified Log-rank test Estimation: Stratified Cox model with Efron's tie handling method	ITT	
Primary censoring ruleSensitivity analysis 1Sensitivity analysis 2Sensitivity analysis 3
Secondary Hypotheses			
OS	Test: Stratified Log-rank test Estimation: Stratified Cox model with Efron's tie handling method	ITT	Censored at the last date the subject was known to be alive

EFS=event free survival; ITT=intention-to-treat; OS=overall survival.
† Statistical models are described in further detail in the text. For stratified analyses, the stratification factors used for randomization (see Section 5.6) will be applied to the analysis model.

8.6.3 Statistical Methods for Safety Analyses

Safety and tolerability will be assessed by clinical review of all relevant parameters including AEs, laboratory tests, and vital signs.

AEs will be summarized overall and by the following time periods:

- Period of treatment with pembrolizumab/placebo in combination with CRT
- Period of maintenance with pembrolizumab/placebo
- Follow-up period with no treatment

The analysis of safety results will follow a tiered approach ([Table 26](#)). The tiers differ with respect to the analyses that will be performed. Adverse events (specific terms as well as system organ class terms) are either pre-specified as "Tier 1" endpoints or will be classified as belonging to "Tier 2" or "Tier 3" based on the number of events observed.

Tier 1 Events

Safety parameters or adverse events of interest that are identified a priori constitute “Tier 1” safety endpoints that will be subject to inferential testing for statistical significance. There are no Tier 1 events for this protocol as preliminary data from the MISP study [67] has demonstrated an acceptable and manageable safety/tolerability profile of pembrolizumab in combination with CRT for LA HNSCC.

Tier 2 Events

Tier 2 parameters will be assessed via point estimates with 95% CIs provided for differences in the proportion of subjects with events.

Membership in Tier 2 requires that at least 10% of subjects in any treatment group exhibit the specific AE; all other AEs will belong to Tier 3. The threshold of at least 10% of subjects was chosen for Tier 2 events because the population enrolled in this study is in critical condition and usually experiences various AEs of similar types regardless of treatment; events reported less frequently than 10% of subjects would obscure the assessment of the overall safety profile and add little to the interpretation of potentially meaningful treatment differences. In addition, 5% of subjects in any treatment group that exhibit a specific serious AE or a specific Grade 3-5 AE will be considered Tier 2 endpoints. Because many 95% CIs for Tier 2 events may be provided without adjustment for multiplicity, the confidence intervals should be regarded as a helpful descriptive measure to be used in review, not a formal method for assessing the statistical significance of the between-group differences in AEs and laboratory values that meet predefined limits of change.

Tier 3 Events

Safety endpoints that are not Tier 1 or 2 events are considered Tier 3 events. The broad clinical and laboratory AE categories consisting of the proportion of subjects with any AE, any drug related AE, any Grade 3-5 AE, any SAE, any AE which is both drug-related and Grade 3-5, any AE which is both serious and drug-related, discontinuation due to an AE, and death that are not pre-specified as Tier 1 endpoints will be classified as belonging to “Tier 3.” Laboratory test toxicity grade shift from baseline is considered Tier 3 event. Only point estimates by treatment group are provided for Tier 3 safety parameters.

Table 26 Analysis Strategy for Safety Parameters

Safety Tier	Safety Endpoint	95% CI for Treatment Comparison	Descriptive Statistics
Tier 2	Specific Grade 3-5 AE (incidence $\geq 5\%$ of subjects in one of the treatment groups)	X	X
	Specific serious AE (incidence $\geq 5\%$ of subjects in one of the treatment groups)	X	X
	Specific AEs, SOCs (incidence $\geq 10\%$ of subjects in one of the treatment groups)	X	X
Tier 3	Any AE		X
	Any Serious AE		X
	Any Grade 3-5 AE		X
	Any Drug-Related AE		X
	Any Serious and Drug-Related AE		X
	Any Grade 3-5 and Drug-Related AE		X
	Discontinuation due to AE		X
	Any AE resulting in death		X
	Specific AEs, surgical complications, SOCs (incidence $> 0\%$ of subjects in one of the treatment groups)		X
	Change from Baseline Results (lab toxicity grade)		X

AE = adverse event; CI=confidence interval; SOC = system organ class.

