3.2 Secondary Objective(s) & Hypothesis(es)

(1) **Objective:** To compare overall survival (OS) in subjects treated with pembrolizumab in combination with CRT and subjects treated with placebo in combination with CRT.

Hypothesis: Pembrolizumab in combination with CRT is superior to placebo in combination with CRT with respect to OS.

(2) **Objective:** To evaluate and compare the safety and tolerability profile of pembrolizumab in combination with CRT and subjects treated with placebo in combination with CRT.

(3) **Objective:** To compare mean change from baseline in Global health status/quality of life (QoL) and physical functioning using the EORTC QLQ-C30, and swallowing, speech and pain symptoms using the EORTC QLQ-H&N35 in subjects treated with pembrolizumab in combination with CRT and subjects treated with placebo in combination with CRT.

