8.1 Statistical Analysis Plan Summary

Key elements of the statistical analysis plan are summarized below; the comprehensive plan is provided in Sections 8.2-8.12.

Study Design Overview	This is a randomized, double-blind, multicenter Phase III trial to evaluate efficacy and safety of pembrolizumab in combination with CRT versus placebo in combination with CRT in subjects with locally advanced HNSCC.
Treatment Assignment	Approximately 780 subjects will be randomized 1:1 into the following two treatment arms: Arm 1 will receive the combination therapy of pembrolizumab 200 mg administered intravenously (IV) every 3 weeks (Q3W) in combination with CRT; Arm 2 will receive placebo Q3W in combination with CRT. Stratification factors are provided in Section 5.6. This study will be conducted as a double-blind study under in-house blinding procedures.
Analysis Populations	Efficacy: Intention to Treat (ITT) Safety: All Subjects as Treated (ASaT)
Primary Endpoint(s)	Event-free survival (EFS)
Key Secondary Endpoints	Overall survival (OS)
Statistical Methods for Key Efficacy/Immunogenicity/ Pharmacokinetic Analyses	The primary hypotheses for EFS will be evaluated by comparing pembrolizumab in combination with CRT to placebo in combination with CRT using a stratified log-rank test. Estimation of the hazard ratio will be done using a stratified Cox regression model. Event rates over time will be estimated within each treatment group using the Kaplan-Meier method.

Statistical Methods for Key Safety Analyses	The analysis of safety results will follow a tiered approach. The tiers differ with respect to the analyses that will be performed. In this trial, no adverse events of interest warrant inference testing as Tier 1 events. Tier 2 parameters will be assessed via point estimates with 95% confidence intervals (CI) provided for between-group comparisons; only point estimates by treatment group are provided for Tier 3 safety parameters. The 95% confidence intervals for the between-treatment differences in percentages will be provided using the Miettinen and Nurminen method with sample size weighting scheme.

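### The overall adverse event categories have no planned between-arm difference with a confidence interval, although the qualifying specific events beneath them do (cheap improvement)

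*Combined protocol and SAP*

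**What the plan says.** Section 3.2 gives the second secondary objective as "To evaluate and compare the safety and tolerability profile of pembrolizumab in combination with CRT" against placebo with CRT. No hypothesis is attached to it.

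Section 8.6.3 sorts safety endpoints into tiers. Tier 1, the tier for inferential testing, is empty in this trial.

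For Tier 2, "Tier 2 parameters will be assessed via point estimates with 95% CIs provided for differences in the proportion of subjects with events". Two thresholds govern entry: "Membership in Tier 2 requires that at least 10% of subjects in any treatment group exhibit the specific AE", and "5% of subjects in any treatment group that exhibit a specific serious AE or a specific Grade 3-5 AE will be considered Tier 2 endpoints". Table 26 applies the 10% threshold to system organ classes as well. The section calls these intervals descriptive and unadjusted for multiplicity.

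The broad categories are assigned to Tier 3 by name. The list covers any AE, any serious AE, any Grade 3-5 AE and the drug-related versions, and it ends "discontinuation due to an AE, and death that are not pre-specified as Tier 1 endpoints will be classified as belonging to" Tier 3. For that tier, "Only point estimates by treatment group are provided for Tier 3 safety parameters". In Table 26 these rows have a mark for descriptive statistics and none for a treatment-comparison interval. The summary in Section 8.1 repeats the rule ("only point estimates by treatment group are provided for Tier 3 safety parameters") and names the Miettinen-Nurminen method, with sample-size weighting, for between-treatment differences.

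**The concern.** An objective to compare safety is normally answered first by a few pooled contrasts: how many more subjects on the experimental arm had a severe event, had a serious event, stopped because of an event, or died of one. These are the rows for which the plan provides no difference and no interval.

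The plan's own reasoning does not explain the choice. Specific terms are tiered by how often they occur, and the 10% threshold is defended on the ground that rarer events add little to interpretation. The broad categories go to Tier 3 whatever their frequency, and no reason is given. Multiplicity is not the obstacle either, since the section already accepts many unadjusted intervals in Tier 2.

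The practical stake is largest for fatal adverse events. If they are spread over many terms, each may stay below the Tier 2 threshold, and no interval for the pooled excess is planned. Overall survival does not fill that gap, because it does not separate fatal toxicity from death from cancer.

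**Working it through.** The plan states no expected rate or precision for any safety category, so there is no figure of its own to reproduce. The check has two parts.

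**1. Which contrasts get an interval**

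| Safety contrast | Place in the plan | Between-arm 95% CI |
|---|---|---|
| Specific AE or system organ class, at least 10% in either arm | Tier 2, Table 26 | Yes |
| Specific serious AE or specific Grade 3-5 AE, at least 5% in either arm | Tier 2, Table 26 | Yes |
| Any Grade 3-5 AE; any serious AE; any drug-related Grade 3-5 AE | Tier 3, Table 26 | No |
| Discontinuation due to AE; AE resulting in death | Tier 3, Table 26 | No |
| All-cause death | Overall survival, Section 8.6.1.2 | Yes (hazard ratio) |

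A subject with a given Grade 3-5 term is also a subject with any Grade 3-5 AE, so the category's incidence is at least that of any term inside it. Once one Grade 3-5 term reaches 5% in an arm, the category has reached it too. The same holds for serious AEs. On the plan's incidence criterion the total would qualify whenever a component does.

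**2. How precise the missing intervals would be**

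Inputs:
- Section 2.1: about 780 subjects randomized 1:1, so 780 / 2 = 390 per arm.
- Assumption: the safety population (Section 8.5.2, all randomized and dosed) is close to that size.
- Assumption: all incidences below.

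Method: unstratified Miettinen-Nurminen. For a difference d, with N = n1 + n2,

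z(d) = (p1 − p2 − d) / √{[p̃1(1 − p̃1)/n1 + p̃2(1 − p̃2)/n2] × N/(N − 1)},

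where p̃1 and p̃2 are the maximum likelihood proportions constrained to differ by d. The limits are the values of d at which z(d) = ±1.96.

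| Subjects with event (of 390 per arm) | Incidence | Difference, points | 95% CI |
|---|---|---|---|
| 20 vs 20 | 5.1% each | 0.0 | −3.2 to 3.2 |
| 39 vs 39 | 10% each | 0.0 | −4.3 to 4.3 |
| 78 vs 78 | 20% each | 0.0 | −5.6 to 5.6 |
| 156 vs 156 | 40% each | 0.0 | −6.9 to 6.9 |
| 195 vs 195 | 50% each | 0.0 | −7.0 to 7.0 |
| 39 vs 20 | 10% vs 5.1% | 4.9 | 1.2 to 8.7 |
| 234 vs 195 | 60% vs 50% | 10.0 | 3.0 to 16.9 |

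With equal arms the half-widths are symmetric about 50%: 80% gives 5.6 points, and about 95% gives 3.2. A hand check with the simple Wald formula at 10% each gives 1.96 × √(2 × 0.10 × 0.90 / 390) = 0.042, or 4.2 points, against 4.3.

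The half-widths therefore run from about 3 to about 7 points.

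**The case against.** The best defence is that this is a deliberate and consistent reporting convention. The safety objective has no hypothesis, Section 8.6.3 rests safety on clinical review, and even the Tier 2 intervals are offered as description. Sections 8.1 and 8.6.3 and Table 26 agree with one another. No error rate and no confirmatory conclusion is affected. All of that stands, and it is why the point is an improvement and not an error.

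A second defence is that anyone with the by-arm counts can compute an interval. This is partly right: crude unstratified intervals follow directly, as shown above. It does not fully answer the point. The plan's method carries a sample-size weighting scheme, whose results overall counts by arm may not reproduce, and a comparative objective is better served when its main contrasts are set out in the plan.

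Three stronger readings are tempting, and the documents support none of them:
- **That safety has no between-arm interval at all.** Tier 2 provides them for specific events and system organ classes above the thresholds.
- **That death is not compared.** All-cause death is, through the overall survival hazard ratio and its 95% CI. Only AE resulting in death lacks an interval.
- **That the omission hides an important excess of toxicity.** The documents give no expected rates for these categories. The incidences above show precision only and are not evidence of harm.

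**Conclusion.** The point holds as a cheap improvement. Any Grade 3-5 AE, any serious AE, any drug-related Grade 3-5 AE, discontinuation due to AE and AE resulting in death have by-arm percentages but no planned between-arm difference with an interval, although the objective is to compare safety and qualifying specific events receive one.

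The intervals would be narrow enough to inform a benefit-risk discussion. That size rests on about 390 treated subjects per arm, an unstratified calculation and assumed incidences. The supplemental SAP and the DMC charter were not available, so it is not known whether either already adds these intervals.

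**What to change.** In Section 8.6.3, Table 26 and the Section 8.1 summary, keep the by-arm percentages for the five categories named above and add the between-arm difference with the Miettinen-Nurminen 95% interval already specified. Label it descriptive and unadjusted for multiplicity, as for Tier 2.

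Amendment 08 states that the final efficacy analysis has been completed, so this can no longer count as prespecified. Record it in the supplemental SAP or the clinical study report as a post hoc addition.

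The cost is a few table entries, with no new data and no alpha. The downside is a few more unadjusted descriptive intervals, which the label should make plain.

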8.6.4 Statistical Methods for PRO Analyses: EORTC QLQ-C30 & QLQ-H&N35

The change from baseline in the following secondary QoL outcomes from the EORTC QLQ-C30 and QLQ-H&N35 will be assessed:

- EORTC QLQ-C30 Global health status/QoL score
- EORTC QLQ-C30 physical functioning score
- QLQ- H&N35 Swallowing symptom score
- QLQ- H&N35 Speech symptom score
- QLQ-H&N35 Pain symptom score

The time point for the mean change from baseline will be determined based on blinded data review prior to the database lock for any PRO analysis and documented in the sSAP. To assess the treatment effects on the quality-of-life outcomes, a constrained longitudinal data analysis (cLDA) model will be applied, with the PRO score as the response variable, and treatment, time, the treatment by time interaction and stratification factors as covariates. The treatment difference in terms of least square (LS) mean change from baseline will be estimated from this model together with 95% CI. Model-based LS mean with 95% CI will be provided by treatment group for PRO scores at baseline and post-baseline time point.

Details of PRO analyses will be described in the sSAP.

8.6.5 Summaries of Demographic and Baseline Characteristics

The comparability of the treatment groups for each relevant characteristic will be assessed by the use of tables and/or graphs. No statistical hypothesis tests will be performed on these characteristics. The number and percentage of subjects screened and randomized, and the primary reasons for screening failure and discontinuation will be displayed. Demographic variables (e.g., age), baseline characteristics, primary and secondary diagnoses, and prior and concomitant therapies will be summarized by treatment either by descriptive statistics or categorical tables.

8.7 Interim Analyses

Study enrollment is likely to be complete at the time of the efficacy interim analysis. Blinding to treatment assignment will be maintained at all investigational sites. The results of interim analyses will not be shared with the investigators prior to the completion of the study. Subject-level unblinding for the interim analysis will be restricted to an external unblinded statistician and scientific programmer performing the interim analysis, who will have no other responsibilities associated with the study.

The eDMC will serve as the primary reviewer of the results of the interim analyses and will make recommendations for discontinuation of the study or modification to the executive oversight committee of the Sponsor. If the eDMC recommends modifications to the design of the protocol or discontinuation of the study, this executive oversight committee and potentially other limited Sponsor personnel may be unblinded to results at the treatment level in order to act on these recommendations. The extent to which individuals are unblinded with respect to results of interim analyses will be documented by the unblinded team. Additional logistic details will be provided in the eDMC Charter.

Treatment-level results of the interim analysis will be provided by the unblinded statistician to the eDMC. Prior to final study unblinding, the unblinded statistician will not be involved in any discussions regarding modifications to the protocol or statistical methods, identification of protocol deviations, or data validation efforts after the interim analyses.

